2 BACKGROUND

Fatigue in Adolescents and Young Adults (AYAs) with Cancer

Fatigue is one of the most prevalent and severe symptoms in adolescents and young adults (AYAs) with cancer.² Defined as “a distressing, persistent, subjective sense of physical, emotional, and/or cognitive tiredness or exhaustion related to cancer or cancer treatment that is not proportional to recent activity”²⁰ (p1), cancer-related fatigue causes significant distress for AYAs and interferes with physical activities, social function, and mood.^{2, 21} AYAs commonly report that fatigue occurs with other troubling symptoms, such as poor sleep, nausea, and pain, and within these symptom clusters, fatigue is frequently named as the priority symptom.²² AYAs with cancer have shown greater symptom severity, including fatigue, than children and older patients.^{23, 24} The higher level of fatigue in AYAs may be due to their accelerated physical and cognitive growth, hormone-related changes, as well as their involvement in multiple activities of this developmental period (school, work, relationships, and parenting).³

Cancer-related fatigue is worst during the treatment period.^{2, 25} During cycles of chemotherapy, fatigue levels may follow a predictable and fluctuating pattern of increasing in the days after each cycle but improving before the next cycle.^{2, 26} Studies also show that fatigue may be a persistent long-term problem, even for AYAs who have completed treatment.^{2, 27, 28}

Physical Activity as an Evidence-based Intervention to Manage Fatigue in AYAs

Major oncology professional organizations recommend physical activity as an evidence-based intervention to manage fatigue, although most of this evidence comes from studies with adults who have the most common cancers, such as breast and prostate cancer.²⁹ Diverse PA programs for people with cancer have included aerobic and muscle-strengthening activities, such as walking, cycling, and yoga, and most programs last between 5 and 12 weeks.³⁰⁻³³

No trials have examined a PA intervention with YAs currently receiving treatment, and minimal PA studies have been conducted with patients who have the common diagnoses of this age group, such as lymphoma, leukemia, sarcoma, and germ cell tumors. A few PA interventions have targeted young adults with cancer who have completed cancer treatment, confirming that these patients are interested and able to participate in PA programs, especially when recommended by PA experts.³⁴⁻³⁶

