3 STUDY DESIGN

General description

The “Step-Up” Study will use a randomized experimental design to examine the preliminary efficacy of the physical activity intervention in AYAs who are receiving chemotherapy that will last approximately 12 weeks.

Number of Subjects

Seventy-five AYAs will be recruited from the Froedtert Hospital/Medical College of Wisconsin (FH/MCW) Cancer Center and Children’s Hospital of Wisconsin.

Primary Endpoints

The primary endpoints for the study include self-efficacy for physical activity, self-regulation of physical activity fatigue severity, physical activity, and fatigue severity.

The following table summarizes the proposed instruments for the study:

IFSMT factor	Variable	Measure	Pre	Post
Condition-specific: Individual	Demographics, health history, diagnosis, treatment regimen	Medical Record Review Form	x	
Condition-specific: Individual and family	Individual, household and family characteristics	Individual and Family Information Form	x	
Condition-specific: Individual	Usual amount of PA before diagnosis (self-reported)	Godin Leisure Time Index ⁴¹	x	
Process: Self efficacy	Self-efficacy for PA	Physical Activity Assessment Inventory ⁴²	x	x
Process: Goal-setting and self-monitoring	Self-regulation skills and abilities	Self-Regulation Index for PA ⁴³	x	x
Process: Negotiated collaboration	Perceptions of the intervention, preferred features of the PA tracker and facilitator	Evaluation of Intervention (intervention group only)		x
Proximal outcome: PA behaviors	# days worn, daily and weekly goals, daily step counts	PA and use of PA tracker (Fitbit) (intervention group only)	throughout	
Proximal outcome: PA behaviors	PA (steps/day)	Blinded accelerometer (ActiGraph GTx3+) x 7 days	x	x
Distal outcome: Symptom severity	Intensity of emotional distress, fatigue, pain, physical function, sleep disturbance, satisfaction with participation in social roles	PROMIS-29 ⁴⁴	x	x
Distal outcome: Fatigue severity	Fatigue frequency, duration, intensity and impact of fatigue on activities	PROMIS – Fatigue Short Form ⁴⁴	x	x

Randomization

Patients will be randomized into two groups (intervention and usual care) using the Excel 'RAND' function to create a randomization chart forcing 38 into the intervention arm and 37 into the usual care arm.

Study Timeline

Primary Completion

The study will reach primary completion 19 months from the time the study opens to accrual.

Study Completion

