6. STATISTICAL ANALYSIS

Sample Size

In an a priori power analysis using a mediation model that includes 4 predictors (intervention variable, self-efficacy, self-regulation, and PA), a total sample of 68 participants (34 in each group) would be needed to detect a medium-sized effect at a 0.10 significance level with 80% power. The power analysis was completed by using an online sample size calculator (<http://www.danielsoper.com/statcalc/calculator.aspx?id=1>) based on the above information. Physicians at FH/MCW and CHW saw approximately 300 AYAs with a new cancer diagnosis in 2012, and about half of those AYAs received chemotherapy. Assuming a 50% enrollment rate and 10% attrition, 75 AYAs will be recruited from these sites for a final sample of 68.

Data Management and Analysis

Questionnaire data will be collected electronically using REDcap surveys, and accelerometer (Actigraph) data will be analyzed using respective software. For the intervention group, weekly PA data will be transcribed from the PA tracker (Fitbit Flex) dashboard to REDcap files at each visit. All REDcap data will be exported to SPSS for analysis. Descriptive statistics will be used to describe and summarize the context variables related to the sample. Variables with significant patterns of variation will be explored as potential covariates. Missing values will be identified and reviewed for patterns of missingness, and the percentage of missing data will be calculated. If missing data are less than 5%, pairwise deletion will be used in data analysis, meaning all available cases will be used. If missing data are greater than or equal to 5%, Little's Chi-square test will be used to check if data are missing at random. If missing at random is assumed, multiple imputation method will be used. Field notes from sessions with the facilitator related to barriers and self-management strategies as well as notes from post-study debriefing interviews will be recorded and organized by participant visit.

After all study queries and analyses are completed, the data/PHI will not be destroyed but will be archived in a secure long-term storage site in order to keep an accurate record of screened and enrolled subjects for the sponsor and potential audit purposes only specific for this study. Data/PHI would not be destroyed until permission is granted by the sponsor to destroy the records.

Statistical Analyses

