Specific Aim 1: To determine the impact of the PA intervention on the self-management process variables of self-efficacy and self-regulation, data analysis will examine differences in baseline and post-study measures of self-efficacy and self-regulation for each group. Group differences will be compared using t-tests to determine the effect of the intervention on these process variables. A mediation model will be used to describe the relationships of self-management process variables (self-efficacy and self-regulation) to PA (steps/day by accelerometer) and fatigue severity where self-efficacy and self-regulation are the main mediators of the intervention, PA is the second mediator, and fatigue severity is the dependent variable. The direct and indirect effect of treatment on PA and fatigue severity will be determined by the following steps:^{45, 46}

- Step 1. The regression of the fatigue severity on the intervention variable, ignoring the mediators, is significant.
- Step 2: The regression of the main mediators on the intervention variable is significant.
- Step 3: The regression of the second mediator (PA) on the main mediators (self-efficacy and self-regulation), controlling for the intervention, is significant.
- Step 4: The regression of the fatigue severity on the second mediator (PA), controlling for the main mediators (self-efficacy and self-regulation) and the intervention, is significant.
- Step 5: The regression of the fatigue severity on the intervention, controlling for the mediators, is non-significant and nearly-zero. In this case, the effect of intervention on fatigue severity is indirect through the mediators. If regression of the fatigue severity on the intervention, controlling for the mediators, is still significant, then the effect of treatment on fatigue severity is direct.

From the regression models, unstandardized regression coefficients and their standard errors will be calculated for the associations between the intervention variable and the mediators as well as between the fatigue severity and the mediators. The Sobel test will be used to test if the mediation effect is statistically significant.⁴⁵⁻⁴⁹ Data from field notes from the intervention group participants will be analyzed using qualitative, inductive content analysis procedures to identify themes related to self-efficacy and self-regulation skills.

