Specific Aim 2: To determine the preliminary efficacy of the PA intervention on outcome variables of PA (steps/day by accelerometer) and fatigue severity, data analysis will examine differences in baseline and post-study measures of PA (steps/day by accelerometer) and fatigue severity (PROMIS-29 and PROMIS Fatigue scores) for each group. Group differences will then be compared using t-tests to detect the effect of the PA intervention on these outcomes. Direct and indirect effect of the intervention on fatigue severity will be studied using the mediation model discussed in Aim 1. Quantitative data about the fidelity of the intervention will be used to estimate the dose of the delivered intervention for each participant and to explore whether there was a dosage effect on the outcomes.

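### Aims 1 and 2 compare arms with t-tests although every tested measure has a baseline value; a pre-specified baseline-adjusted regression would be more precise, and the mediation model should name its scores

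*Combined protocol and SAP*

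**What the plan says.** Section 6, Specific Aim 2, states that "data analysis will examine differences in baseline and post-study measures of PA (steps/day by accelerometer) and fatigue severity" for each group, and then: "Group differences will then be compared using t-tests to detect the effect of the PA intervention on these outcomes". Specific Aim 1 has the same structure for the process variables: "Group differences will be compared using t-tests to determine the effect of the intervention on these process variables". Neither aim says whether the t-test is applied to change scores or to post-study scores.

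The instrument table in Section 3 marks self-efficacy, self-regulation, PROMIS-29, PROMIS Fatigue and accelerometer steps/day ("Blinded accelerometer (ActiGraph GTx3+) x 7 days") as both pre and post. The only rule on covariates is in Section 6, Data Management and Analysis: "Variables with significant patterns of variation will be explored as potential covariates". It does not mention the baseline value of the outcome.

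For mediation, Step 4 regresses fatigue severity on PA, "controlling for the main mediators (self-efficacy and self-regulation) and the intervention, is significant". Steps 1 to 5 name arm and mediators only. They do not say which scores enter, and they include no baseline term.

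**The concern.** With a continuous outcome measured before and after a randomised intervention, regression of the post value on arm and its own baseline is, in large samples, at least as precise as a t-test on either change or post scores. The plan collects the data for this analysis and does not specify it. With about 68 evaluable participants and an aim of preliminary efficacy, the lost precision could have been had at almost no cost. Leaving the score unnamed, with covariates to be explored later, also leaves a choice open after the data are seen.

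The mediation model raises a different issue. Arm is randomised; PA, self-efficacy and self-regulation are not. Participants who enter the study less active and more fatigued may still be so at the end. If unadjusted post-study scores were used, that difference alone could appear as a PA-fatigue association.

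**Working it through.** **The plan's own figure.** Section 6, Sample Size, says that 68 participants "would be needed to detect a medium-sized effect at a 0.10 significance level with 80% power" in a model with 4 predictors. Taking a medium effect as f² = 0.15 (assumed), the overall F test with noncentrality 0.15 × N and N − 5 denominator degrees of freedom has 79.6% power at N = 68 and reaches 80% at N = 69. The figure is reproduced, but it concerns a regression, not the t-tests.

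**Group comparisons: inputs.** From the plan: 34 per arm. Assumed: a true difference d = 0.5 in SD units of the post score, equal variances at both times, a two-sided 10% level (0.10 is stated only for the sample size, without sidedness), and a pre-post correlation ρ of 0.3 to 0.8.

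**Variance relative to the post score.** Post score: 1. Change score: 2(1 − ρ). Baseline-adjusted: 1 − ρ².

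**Noncentrality** = 0.5 × √(34/2) / √(variance factor) = 2.062 / √(variance factor). Degrees of freedom are 66 for the t-tests and 65 for the adjusted analysis; the critical values are 1.668 and 1.669.

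Example at ρ = 0.5: change 2.062/√1.00 = 2.062, power 65.4%; adjusted 2.062/√0.75 = 2.38, power 76.1%.

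| ρ | Factor: change / post / adjusted | Power, 10% level | Gain over change | Power, 5% level |
|---|---|---|---|---|
| 0.3 | 1.40 / 1 / 0.91 | 53.2 / 65.4 / 68.9% | 15.7 points | 40 / 53 / 57% |
| 0.5 | 1.00 / 1 / 0.75 | 65.4 / 65.4 / 76.1% | 10.7 points | 53 / 53 / 65% |
| 0.7 | 0.60 / 1 / 0.51 | 83.9 / 65.4 / 88.7% | 4.8 points | 75 / 53 / 81% |
| 0.8 | 0.40 / 1 / 0.36 | 94.3 / 65.4 / 96.0% | 1.7 points | 90 / 53 / 92% |

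The adjusted variance is (1 − ρ²) / [2(1 − ρ)] = (1 + ρ)/2 of the change-score variance. To match the adjusted analysis on 68 participants, a change-score t-test would need 68 × 2/(1 + ρ), or about 105, 91, 80 and 76 participants at the four correlations.

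**Mediation, Step 4 alone.** This was simulated (20,000 trials per setting) with n = 68, steps/day as the only mediator, no true PA-to-fatigue effect and a nominal 10% level. All correlations are assumed: baseline PA-fatigue correlation −0.3 to −0.5 and stability 0.5 to 0.7. In model A, the post value is ρ × baseline plus independent noise. In model B, stable correlated traits are measured with visit noise.

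| False-positive rate | Unadjusted post | Change | Baseline-adjusted |
|---|---|---|---|
| Model A | 16–64% | 12–16% | 10% |
| Model B | 80–99% | 10% | 14–26% |

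In the mildest model A setting (−0.3, 0.5), post and change scores are level at 16.0% and 15.8%. With all three mediators they are again level there (15.1% and 15.2%). In the other settings of both models, unadjusted post scores are clearly worst. Baseline adjustment holds the nominal level under A; change scores hold it under B.

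**Visit timing.** The Study Calendar puts intervention education and the tracker at Visit 1, where the baseline accelerometer week begins. Section 5 puts them at Visit 2. Under the calendar, the baseline step week could overlap the start of the intervention.

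**The case against.** Baseline is probably not ignored. The wording on differences between baseline and post-study measures points to change scores, and on that reading the gain at the 10% level is only about 5 points at a correlation of 0.7 and 2 points at 0.8. That stands. The 16-point gain needs a correlation as low as 0.3.

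A reader might infer a low correlation from the Background, which says that "fatigue levels may follow a predictable and fluctuating pattern of increasing in the days after each cycle but improving before the next cycle". The documents do not support that step. The pattern is called predictable, and the Visit 6 surveys take place at a scheduled chemotherapy visit. Visit 1 may fall at a similar point in the cycle, though this is not stated. Admitting any cancer diagnosis adds variation between patients, which would tend to raise the correlation. A high value cannot be presumed either, so the full range has to be shown.

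A reader might also infer that the mediation analysis will be badly biased. The plan never says that raw post-study scores enter. The large model B rates mostly restate the assumption that PA and fatigue stay correlated at follow-up. Step 4 is also only one link: the result of the full sequence depends on whether both main mediators, or only one, must be significant in Steps 2 and 3, which the plan leaves open. No error rate for the full sequence can be given from these documents.

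Finally, this is described as an exploratory pilot seeking preliminary efficacy. That limits the severity, but the improvement is still nearly free.

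**Conclusion.** The point holds as one of efficiency and specification. It would be wrong to conclude that the t-tests bias the arm comparison: under randomisation, both change-score and post-score tests are unbiased.

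At an assumed d = 0.5 and two-sided 10% level, baseline adjustment adds about 16, 11, 5 and 2 points of power over change scores at correlations of 0.3, 0.5, 0.7 and 0.8. Over post scores it adds about 4, 11, 23 and 31 points. The textual facts and the variance formulas are firm; the correlation, effect size and test level are assumptions.

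The mediation part is secondary. What is established is that the scores are not named, that randomisation does not protect the mediator-to-outcome paths, and that unadjusted post-study scores are the worst choice, or level with change scores in the mildest setting. Neither baseline adjustment nor change scores is better throughout. The size of any mediation error rests on assumed correlations.

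**What to change.** **Aims 1 and 2.** Replace the t-tests with linear regression of the post-study value on arm and the baseline value of the same measure, named in advance. Report the adjusted difference with its confidence interval. This needs no new data and costs one degree of freedom per test.

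**Condition for steps/day.** Reconcile the Study Calendar with Section 5 on whether intervention education and the tracker start at Visit 1 or Visit 2 before baseline steps/day is treated as pre-intervention.

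**Mediation.** State in advance which scores enter each step, and do not use unadjusted post-study scores. Report both a version with the baseline values of mediators and outcome as covariates and a change-score version, and describe both as associational. In the adjusted version, Step 4 grows from 4 to as many as 8 predictors. With f² = 0.15 (assumed), n = 68 and a 0.10 level, overall-model power falls from 80% with 4 predictors to 73% with 6 and 67% with 8 if the baselines explain nothing. The sample-size text should say so.

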7. ADVERSE EVENTS

Data and Safety Monitoring Plan

a. Monitoring Entity. The Safety Monitoring Committee of the P20 Center, the Self-Management Science Center at UWM, will be responsible for monitoring the data safety of this pilot project. The Safety Monitoring Committee includes the Pilot Core Director ([name]), Pilot Core Methods/Content Expert ([name]), and two members independent of the P20 Center ([name], Biostatistician, and [name], Community and Behavioral Health Promotion). The P20 Center Director ([name]) is responsible for submitting necessary reports to NINR.

b. Procedures

- 1. Monitoring study safety.** The Pilot Project Director ([name]) will meet bi-weekly with the study team to review study enrollment, compliance with IRB requirements, including informed consent, verification of source documents, and compliance with study procedures. The Pilot Project Director will report at the P20 Center Pilot Projects bi-weekly meetings with the Pilot Core Director any concerns related to study safety identified by the project team. At the point when 10% of the participants are enrolled and at random intervals throughout the duration of the study, the Pilot Core Director or Methods Expert will review the informed consents for compliance to IRB requirements. The Pilot Project Director will provide the necessary study documents for review as requested.
- 2. Minimizing research-associated risk.** This pilot project is anticipated to be minimal risk, but potential risks are that participants may experience psychological discomfort or distress when reflecting upon their personal experiences about cancer and cancer-related symptoms and/or physical discomfort, distress, or injury related to following a low-intensity physical activity (PA) plan. The Pilot Project Director ([name]) will investigate any research-associated risks that are identified by the study team members and will report these concerns to the P20 Center Principal Investigator ([name]) or the Pilot Core Director ([name]) so that these concerns can be addressed.

The following actions will be outlined in the study procedures to protect against risks:

Psychological discomfort or distress. The facilitator and other members of the study team will be educated about how to recognize emotional distress and to make every effort to provide psychosocial support when emotional distress is evident. In the event that any participant demonstrates or self-reports a high level of distress, a member of the study team will conduct a further assessment. With the participant's consent, the study team may inform the participant's health care provider of the emotional distress in order to make adjustments to the care plan or suggest referrals for specialized care. No information will be disclosed to another party without the participant's consent unless there is imminent danger to the participant or others.

Physical discomfort, distress, or injury related to following a low-intensity physical activity (PA) plan. According to the American College of Sports Medicine, PA is safe and beneficial for patients during cancer treatment, and baseline exercise-testing is not required for patients to participate in low- to moderate-intensity PA, such as walking or resistance training. We will exclude patients who have contraindications to PA, which may include symptoms of uncontrolled cardiopulmonary disease, uncontrolled neurological disease, delayed wound healing from surgery, a high risk of bone fracture, or preexisting peripheral neuropathy, and we will obtain written approval from the

patient's physician to indicate none of these conditions apply. Patients will receive information from the facilitator about PA safety at the start of the study and will be advised to set PA goals based on their baseline PA level and to respect their own physical limitations. Participants will be reminded to complete 'pre-exercise' screening every day, and they will be advised not to engage in PA if they have any of the following conditions: 1) heart palpitations or chest pain; 2) fever greater than 38o C; 3) shortness of breath at rest; 4) new bruises or ongoing bleeding; 5) uncontrolled pain or nausea; 6) dizziness. They will be advised not to resume PA until these conditions resolve, and they should contact their health care provider about the condition if the problem is new and/or severe. PA studies have been safely carried out with patients undergoing intensive chemotherapy who have platelet values as low as 20,000/mm³ and leucocytes < 1.0X10⁹/L, and no studies have shown PA complications related to bleeding or infection. At each visit, the facilitator will discuss PA safety with each participant, explore any concerns about physical discomfort or distress that may be related to PA, and any new symptoms that may be a contraindication to PA. The facilitator will consult with the patient's care providers if there are any concerns about continuing the PA study.

3. Protecting confidentiality of participant data. Only study team members will have access to participant data. Participant data will be listed using a study ID number, and identifiable personal health information (PHI) will be stored separately from other study data. Data from surveys, accelerometers (Actigraphs), and PA trackers (Fitbits) and from facilitation and interview sessions will be stored on password-protected computers with access limited to study personnel. The Pilot Project Director will monitor all project-related computers and devices used in the study for compliance with data security protocols. Data analyses will be conducted without identifiers. The Pilot Project Director will report any data security issues to the P20 Principal Investigator.

c. Adverse Events and Unanticipated Problems. This pilot project is identified as minimal risk, and adverse events are not expected. The study team will review study activities and participant involvement at each bi-weekly team meeting with attention to identification of any unexpected events or problems. Should an adverse event or unanticipated problem occur, the project team will immediately contact the Pilot Project Director ([name]), who will contact the P20 Center Principal Investigator ([name]). The PI will assess the event or problem and notify the IRB and NINR, including the plan to address the problem.

d. Multi-site Studies. This is not a multi-site study.

e. External Factors. Before each quarterly meeting with the P20 DSM Team, the Pilot Project Director ([name]) and Project Co-Investigators ([name] and [name]) will review any changes in practice or policy at Froedtert Hospital/MCW Cancer Center that would affect this study. They will also review any relevant new literature or research that would impact the safety of the participants or ethics of the study. The Pilot Project Director will present a summary of these relevant external factors at the quarterly P20 Center meetings.

f. Advanced Plan for Analysis. An advanced plan for interim and/or futility analysis is not planned for this pilot project.

g. Subject Complaints. If a complaint is received by anyone on the study staff, it will be discussed with the study staff and will be addressed on a case-by-case basis. The PI will be notified of any complaints. Complaints will be reported to the IRB if indicated.

If the subject has questions about his or her rights as a study subject, wants to report any problems or complaints, obtain information about the study or offer input, the subject can call the Medical College of Wisconsin/Froedtert Hospital research subject advocate at [contact]. This information is provided to the subject in their consent.

The investigator will assess all adverse events and determine reporting requirements to the MCWCC Data and Safety Monitoring Committee (DSMC) and MCW's Institutional Review Board.

